India North. We will focus on 40 surveillance sites located in the South Delhi Municipal Corporation (SDMC), in the Delhi National Capital Region (NCR). SDMC serves a population of ~10M people, with diverse demographics characteristics, and includes both urban and rural villages. The South and Najafgrah zones of SDMC will be classified as one hub, while the Central and West zone will be classified as the second hub. We will compile a list of the basic health care units in each SDMC zone (Appendix 2), and classify each as urban / rural based on governmental data. If a health care unit caters to a large population (>50,000), the area will be divided into smaller colonies of 10-50,000 people. From this compiled list of SDMC locations, we will then select 40 surveillance sites at random, but including urban and rural locations in a 1:1 ratio. The population catered to by the health care units will be mobilised by the ASHA workers affiliated to the established surveillance sites.

India South. We will conduct surveillance in both urban and rural areas. The surveillance sites will be villages in rural areas and census enumeration blocks (CEBs) in urban areas. The ultimate stage units will be households in both areas. The rural component of the surveillance is planned to be conducted in 25 selected villages in Cheyur taluk (Appendix 2), which is situated in Kancheepuram district of Tamil Nadu state in southern India. All individuals who meet the inclusion criteria in each household within the selected villages will be invited to participant in the surveillance (n=20,000).

The urban component of the surveillance will be carried out in Chennai, which has a population of 10,705,000 individuals. Chennai is divided into 15 zones and 200 wards by the Chennai Corporation. Of the 200 wards, 40 wards will be randomly selected to represent all 15 zones of the Corporation of Chennai. From the selected 40 wards, 10 Census Enumeration Blocks (CEBs) will be randomly selected from each ward (n=400). The next stage of sampling will be based on systematic sampling where 50 households from each CEB will be selected

with a random start. One individual will be selected using the WHO KISH method and meets the inclusion criteria in each household will be invited to participant in the surveillance (n=20,000) (Appendix 2).

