4. PARTICIPANT ENTRY

Participants: entry criteria and sample size

All adults South Asian men and women living within the geographic boundaries of the selected surveillance site (as described by the relevant national administrative systems), will be invited to take part in the research. Recruitment targets (participants with appropriate consent, data and samples collected) by region to 2021 are provided in **Table 1**.

Inclusion criteria will be:

- 1. Age 18+ years
- 2. Male or Female
- 3. South Asian ancestry
- 4. Permanent resident of the surveillance site (resident for >12 months)

Exclusion criteria will be:

- Planning to leave the study site within the next 12 months
- Cancer or other serious illness expected to reduce life expectancy to less than 12 months

· Unable or unwilling to give consent

Table 1. Recruitment targets by country / region for the Surveillance study.

Region	Recruitment target	Partner organisations
Bangladesh	30,000	BRAC University, Dhaka
North India	30,000	DDF (Max Healthcare), Delhi
South India	40,000	Madras Diabetes Research Foundation, Chennai
Pakistan	30,000	Service Institute of Medical Science, Lahore Punjab Institute of Cardiology, Lahore King Edward Medical University, Lahore
Sri Lanka	30,000	University of Colombo, Colombo University of Kelaniya, Ragama

Recruitment

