At each study site, governmental census data and other available household listings will be used, supported by house-house visits, to fully enumerate and identify the resident population. House-to-house visits will be done by the local primary care worker, in partnership with the research team. The purpose and potential benefits (personal and societal) of the surveillance will be explained. The research team will then obtain demographic details for the adult population of each household. People eligible and consenting to take part in the surveillance study will be asked to attend a nearby health facility in the fasting state, for the surveillance health assessment. Explanations of the project will be provided in writing and using videos, available in relevant South Asian languages, and supported by bilingual translators. We will also engage the community elders (eg teachers, employers, religious leaders) as trusted third parties, to support and facilitate engagement of the community in the study. Based on previous experience with population studies in these communities, participation rates are expected to exceed >70%; the availability of household enumeration data will enable participation to be monitored in detail, including by age, gender and major socio-economic groups.

Study procedures

Participants will be asked to attend in the morning after an overnight fast (water only after midnight). All participants will complete a structured assessment by trained members the dedicated research team, in five complementary domains: i. Registration and consent; ii. Questionnaire; iii. Physical measurements; iv. Biological samples and v. Clinical reporting. All study procedures implemented represent well established tools, that are validated for assessment of NCDs in population studies. The procedures will be carried out by trained research staff, using equipment and protocols that are standardized between countries and surveillance sites.

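### South India's target of 40,000 completed participants equals the number of people to be invited, so it is met only at 100% participation, while the protocol expects only more than 70%

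*Protocol*

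**What the plan says.** The protocol's Section 3 (Selection of Surveillance sites, India South) describes two components, each labelled n=20,000.

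- **Rural, 25 villages in one taluk:** "All individuals who meet the inclusion criteria in each household within the selected villages will be invited to participant in the surveillance (n=20,000".
- **Urban, Chennai:** "Of the 200 wards, 40 wards will be randomly selected to represent all 15 zones of the Corporation of Chennai"; then "10 Census Enumeration Blocks (CEBs) will be randomly selected from each ward (n=400"; then "systematic sampling where 50 households from each CEB will be selected". The sentence on the last stage begins "One individual will be selected using the WHO KISH method and meets the inclusion criteria in each household will be invited to participant in the"; it too carries the label n=20,000.

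Section 4 (Participant entry) introduces Table 1 as "Recruitment targets (participants with appropriate consent, data and samples collected) by region to 2021". The South India row is 40,000; the other four regions have 30,000 each.

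Section 4 (Recruitment) states that "participation rates are expected to exceed >70" per cent, citing experience with population studies in these communities.

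For South India the protocol describes no reserve households, oversampling or additional villages or blocks.

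**The concern.** The same number does two jobs. In Section 3 it counts people who receive an invitation. In Table 1 it counts people who have consented, attended and given data and samples. The two can be equal only if nobody declines and, in Chennai, only if every sampled household also contains an eligible adult.

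South India has the largest regional target in Table 1, and the sampling plan as written does not deliver it. At stake are a recruitment target that cannot be met as described and a regional sample smaller than the one announced. It also leaves open how the study total of ~160,000 is to be reached.

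**Working it through.** **Inputs**

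- Urban stages: 40 wards, 10 blocks per ward, 50 households per block, 1 person per household (Section 3, India South).
- Rural: n=20,000, attached to people invited (same section).
- Target: 40,000 completed participants for South India, 30,000 for each of four other regions (Section 4, Table 1).
- Participation: more than 70% (Section 4, Recruitment). This is a floor, not a point estimate.

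**Step 1: reproduce the plan's figures**

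- Urban invitations: 40 × 10 × 50 × 1 = 20,000, exactly the stated n.
- Region: 20,000 + 20,000 = 40,000, exactly the Table 1 target.
- Study: 4 × 30,000 + 40,000 = 160,000, exactly the stated total.

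The urban 20,000 is the plain product of the sampling stages, so it contains no allowance for refusal. The target is reproduced only with participation of 100%.

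**Step 2: yield = invitations × participation**

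Reading A takes both 20,000s as invitees: yield = 40,000 × r. Reading B takes the rural 20,000 as recruits: yield = 20,000 × r + 20,000.

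| Participation r | Urban arm | Region, reading A | Region, reading B |
|---|---|---|---|
| 70% (floor) | 14,000 | 28,000 | 34,000 |
| 80% | 16,000 | 32,000 | 36,000 |
| 90% | 18,000 | 36,000 | 38,000 |
| 100% | 20,000 | 40,000 | 40,000 |

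**Step 3: study total, if the other four regions recruit exactly 120,000**

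- At 70%: 120,000 + 28,000 = 148,000 (A) or 120,000 + 34,000 = 154,000 (B), a gap of 12,000 or 6,000 (7.5% or 3.8% of 160,000).
- At 80%: 152,000 or 156,000.

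**Step 4: is there headroom elsewhere?**

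Sri Lanka has 100 sites × 500 eligible people = 50,000 for a target of 30,000, so 60% participation is enough. At 70% it would give 35,000, which is 5,000 above target. Counting that surplus, the study total at the floor becomes 153,000 (A) or 159,000 (B).

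**Step 5: effect on Table 4**

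The 95% half-width is 1.96 × √(p(1−p)/N), taking simple random sampling. At p = 30%:

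- N = 160,000: 0.225%; N = 148,000: 0.233%. Both print as the tabulated 0.2%.
- N = 28,000 (South India at the floor, reading A): 0.537%, which still prints as the 0.5% in the country column. That column already uses N = 30,000, not 40,000.

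The detectable odds ratio at 30% prevalence (20% exposed, 90% power, two-sided 5%) is 1.045 at N = 160,000 and 1.047 at N = 148,000.

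**Step 6: invitations needed to keep the target at 70%**

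- Urban: 20,000 / 0.70 ≈ 28,572 invitations; divided by 400 blocks this is 71.4, so 72 households per block. 72 × 400 = 28,800 invitations, and 28,800 × 0.70 = 20,160.
- Region under reading A: 40,000 / 0.70 ≈ 57,143 invitations.

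**The case against.** The best case for the plan has four parts.

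1. **70% is a lower bound.** This stands: 14,000 and 28,000 are the low end of what the protocol expects, not its forecast. But any rate below 100% still misses the target.
2. **The rural n may mean recruits.** The sentence attaches the number to an invitation, but a loose parenthesis could give the expected yield. This stands as an ambiguity and is why the regional range extends to 34,000. It does not help the urban arm, where the number is fixed by the sampling stages.
3. **Other regions may make up the difference.** A reader might infer that the study will end at 148,000 to 154,000. The protocol does not support that as a firm result: it nowhere caps the other regions at their targets, Sri Lanka has clear headroom, and the total is given as approximate. The regional mismatch does not depend on this.
4. **Little precision is lost.** This also stands. A reader might infer that Tables 4 and 5 are undermined. Table 4 hardly moves. Table 5's case counts do not rest on 160,000 in any case: 8,550 diabetes cases in 5 years at 950 per 100,000 per year imply 8,550 / 0.0475 = 180,000 people. A lower South India figure would not correct that table.

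A reader might also infer that the probability sample will be compromised by replacing households or taking second household members to fill the gap. The protocol describes no such practice, and rules for non-response may sit in a sampling manual or analysis plan that is not shown. That risk is hypothetical.

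**Conclusion.** The point holds at the level of the region. South India's 40,000 completed participants equal the 40,000 people to be invited, so the target requires full participation, against a stated expectation only of more than 70%. It is firmest for Chennai: 20,000 invitations give about 14,000 participants at the floor. For the region the floor yield is about 28,000 or 34,000, depending on how the rural figure is read.

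The consequence for the ~160,000 total is conditional. The gap of 6,000 to 12,000 applies at 70% participation with every other region exactly on target; it shrinks with higher participation or a surplus elsewhere. The yields also assume that every sampled urban household has an eligible adult and that the plan contains no oversampling or replacement beyond what the protocol describes. This is a recruitment figure that the design does not deliver, with little effect on overall precision or power.

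**What to change.** 1. In Section 3, state for each n=20,000 in South India whether it counts people invited or people recruited.
2. Restate the South India row of Table 1 as invitations × expected participation: at least about 28,000 (both figures invitees) or 34,000 (rural figure recruits) at the 70% floor, with the participation rate shown.
3. Qualify the ~160,000 total where it appears, saying that it depends on participation in South India and on recruitment in the other regions.

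These are text changes and cost nothing.

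If 20,000 urban participants are to be kept at 70% participation, the alternative is to draw about 72 households per block at the outset (28,800 invitations instead of 20,000). That means 22 more households in each of 400 blocks, or 8,800 additional household contacts, and it repairs only the urban half. If the rural figure also counts invitees, the rural arm would need a matching increase. Restating the target is the cheaper course.

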We will study at least 40 surveillance sites in each of the 5 study regions (Bangladesh, India North, India South, Pakistan, Sri Lanka; N>200 sites in total). Selection of sites will be done in such a way that we are able to generate credible estimates on burden of CVD and T2D, and their risk factors from a sample that are representative of the country, rural and urban areas separately and for each of the major administrative regions. In outline, site selection for each country/region will be as follows:

Bangladesh. We will select 42 sites, distributed across the entire country (**Appendix 2**). Bangladesh has 8 divisions, with substantial variation in population size between divisions. In addition, the Chittagong Hill Tracts (CHT), which comprise 3 districts, are different from the rest of Bangladesh with respect to population density and ethnicity. We will select 40 surveillance sites from the 8 divisions (excluding the CHT), with the number of surveillance sites in each division being proportionate to the population size of the division. In addition, we will chose a further 2 surveillance sites from CHT (thus N=42 total). The number of rural and urban sites within a division will be proportional to the rural and urban population with a condition that there will be at least 1 urban site in each of the division. The CHT will have 2 rural sites.

The surveillance sites will be selected using a multistage sampling approach. For the selection of rural sites we will randomly select one district from each division and the CHT. We will then randomly select one sub-district from the district/CHT. Afterwards, one or more community clinics (CC) will be selected from the respective sub-district depending on the number of rural sites within the district. The ward in which the CC is located will be our rural surveillance site. For the selection of urban sites, one urban dispensary (UD)/CC will be randomly selected from each of the 12 city corporations. The *mahalla* in which the UD/CC is located will be the urban surveillance site. If the ward/mahalla is too large and has more than 2000 population, we will divide the ward/mahalla into segments. The segment that has the CC/UD will be our surveillance site. Everyone who meets the inclusion criteria within the selected site will be recruited in the surveillance.

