Pakistan. Pakistan has a population of ~214M people, and is divided administratively into four provinces (Balochistan, Punjab, Sindh, Khyber Paktunkhwa) and the Islamabad Capital Territory (ICT). Each province is further divided into divisions, towns and union councils. The union council is the smallest division, and typically consists of ~30,000 people. Each union council has basic health unit and outreach staff. The union council will be our sampling unit for surveillance.

We will focus the surveillance project on the Punjab Province, the most populated state of the country (N=110M). We will aim to establish surveillance sites in each of the 36 states that comprise the Punjab Province, distributed between in proportion to population size, with approximately 1 site per 3 million population. Surveillance sites will be selected using a multistage sampling approach. During the first stage, target towns will be selected for each province, based on population size of the province (one town per 5-6 sites). In each town, the available administrative lists of union councils will be used to select rural and urban union councils in a 1:1 ratio. As stage 1, surveillance will start in central Punjab (Appendix 2), and will be extended to North and South Punjab on successful completion of stage 1.

Sri Lanka. Sri Lanka has 9 Provinces, that are in turn divided administratively into 25 Districts, and then into further administrative units of which the smallest is the Grama Niladhari (GN). We will select 100 surveillance sites from all the districts and provinces. Each site will have 500 persons eligible to be a participant of the surveillance. The number of surveillance sites for each province will be proportionate to the population size of the province. The number of sites for each district within a province will again be proportionate to the population size of the district. Within a district we will allocate the surveillance sites based on the proportion of rural and urban population. The provisional allocation of surveillance sites by district and province is summarized in Appendix 2.

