Table 2.5. Sri Lanka sample design

Province and district	Population ('000)	Proportion of SL total	No of Clusters allocated	Distribution of clusters		
				Urban	Rural	Estate
Western	5851	28.7	28			
Colombo	2324		12	9	3	
Gampaha	2305		10	2	8	
Kalutara	1222		6	1	5	
Central	2572	12.6	12			
Kandy	1375		6	1	5	
Matale	485		2	0	2	
Nuwara-eliya	712		4		2	2
Southern	2477	12.1	12			
Galle	1063		6	1	5	
Matara	814		4	1	3	
Hambantota	600		2		2	
Northern	1061	5.4	6			
Jaffna	584		2		2	
Mannar	100		1		1	
Vavuniya	172		1		1	
Mullaitivu	92		1		1	
Kilinochchi	114		1		1	
Eastern	1556	7.6	8			
Batticaloa	527		3	1	2	
Ampara	649		3	1	2	
Trincomalee	380		2		2	
North-western	2381	11.7	12			
Kurunegala	1618		8		8	
Puttalam	762		4		4	
North-central	1267	6.2	6			
Anuradhapura	861		4		4	
Polonnaruwa	406		2		2	
Uva	1266	6.2	6			
Badulla	815		4		3	1
Monaragala	451		2		2	
Sabaragamuwa	1929	9.5	10			
Ratnapura	1088		6	1	5	
Kegalle	841		4		4	
				18	79	3

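### Sri Lanka's within-district urban/rural split has no urban minimum, so the provisional Table 2.5 gives any urban residents of 16 of 25 districts, including every district of four provinces, no chance of selection

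*Protocol*

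**What the plan says.** Section 3 of the Protocol (Selection of Surveillance sites) sets one aim for all countries: estimates from a sample "representative of the country, rural and urban areas separately and for each of the major administrative regions".

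For Sri Lanka it notes that "Sri Lanka has 9 Provinces, that are in turn divided administratively into 25 Districts" and plans 100 sites, shared among provinces and then districts by population size. The last step is the urban/rural split: "Within a district we will allocate the surveillance sites based on the proportion of rural and urban population". No minimum number of urban sites is set for a district or a province. The Bangladesh paragraph does set one, requiring "at least 1 urban site in each of the division".

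The result is in Appendix 2, Table 2.5. The text describes its status: "The provisional allocation of surveillance sites by district and province is summarized in Appendix 2". Appendix 2 is itself headed as a draft. Section 7 says that sample weights will be used in the descriptive analysis.

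**The concern.** A district has between 1 and 12 clusters. Splitting so few by urban share and rounding sets the urban number to zero wherever that share is modest. A stratum with no cluster has selection probability zero. Weights can rebalance strata that were sampled, but they cannot stand in for one that was not.

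Two of the protocol's targets are affected. The national urban estimate would leave out every town in the districts without an urban cluster. In provinces where no district has one, the provincial estimate would describe rural (in Uva, rural and estate) residents while carrying the province's name. For a condition more common in towns such an estimate is too low, and for one less common it is too high. Recruiting more people at the same sites does not reduce this error.

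**Working it through.** **Step 1. Are the blank cells true zeros?** In all 25 rows of Table 2.5, urban + rural + estate equals the district's allocation. The columns give 18 + 79 + 3 = 100, matching the printed totals. The blanks are zeros.

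**Step 2. Where are the 18 urban clusters?** Colombo 9, Gampaha 2, and one each in Kalutara, Kandy, Galle, Matara, Batticaloa, Ampara and Ratnapura: 9 + 2 + 7 = 18, in nine districts and five provinces.

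**Step 3. Where are there none?** (populations in thousands, from Table 2.5)

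- Four provinces: Northern 1,061 + North-western 2,381 + North-central 1,267 + Uva 1,266 = 5,975. This is 5,975/20,360 = 29.3% of the population, with 6 + 12 + 6 + 6 = 30 clusters in 11 districts.
- Five districts elsewhere: Matale 485 + Nuwara-eliya 712 + Hambantota 600 + Trincomalee 380 + Kegalle 841 = 3,018.
- All 16 districts: 5,975 + 3,018 = 8,993, or 8,993/20,360 = 44.2%.

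**Step 4. How large can the missed urban population be?** The protocol gives no urban shares. Assume nearest-integer rounding. Zero urban clusters out of n then implies an urban share below 0.5/n: 50% for 1 cluster, 25% for 2, 12.5% for 4 and 6.25% for 8. Ceilings by province (thousands):

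| Province | Sum of population x ceiling | Maximum urban share |
|---|---|---|
| North-western | 1,618 x 0.0625 + 762 x 0.125 = 196.4 | 196.4/2,381 = 8.2% |
| North-central | 861 x 0.125 + 406 x 0.25 = 209.1 | 209.1/1,267 = 16.5% |
| Uva | 815 x 0.125 + 451 x 0.25 = 214.6 | 214.6/1,266 = 17.0% |
| Northern | 584 x 0.25 + (100 + 172 + 92 + 114) x 0.5 = 385.0 | 385.0/1,061 = 36.3% |

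The four sum to about 1,005 thousand. The five other districts add 485 x 0.25 + 712 x 0.125 + 600 x 0.25 + 380 x 0.25 + 841 x 0.125 = 560.4, giving about 1,566 thousand (7.7% of the population). These are upper limits, not estimates.

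**Step 5. Bias.** Bias = u x d, where u is the urban share left out and d the urban-minus-rural difference in prevalence. Assume d = 5-10 points.

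- North-western at its ceiling: 0.082 x 5 to 10 = 0.4-0.8 points.
- North-central and Uva at their ceilings: 0.165-0.170 x 5 to 10 = 0.8-1.7 points.
- Northern: 1.0-2.0 points at an assumed 20% urban share. Rounding bounds it only weakly, and at the 36.3% ceiling it would be 1.8-3.6.
- National, four provinces: 1,005/20,360 = 4.9%, so 0.2-0.5 points. All 16 districts: 7.7%, so 0.4-0.8 points. Both use ceilings everywhere at once.

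**Step 6. Compare with sampling error at the same level.** Half-width = 1.96 x sqrt(DEFF x p(1-p)/n), where DEFF is the design effect. The protocol's country figure comes first: p = 20% and n = 30,000 give 0.45 points, which Table 4 prints as 0.5%. For a province, take 300 people per site (30,000/100 from Table 1) to 500 (the eligible persons per site in Section 3):

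- 6 clusters, n = 1,800-3,000: 1.4-1.9 points with DEFF 1, and 2.0-2.6 with DEFF 2.
- 12 clusters (North-western), n = 3,600-6,000: 1.0-1.3 with DEFF 1, and 1.4-1.9 with DEFF 2.

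The bias in North-western lies inside this range of error. In North-central and Uva it is at most about as large as the error. Only Northern near its ceiling would clearly exceed it.

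**The case against.** The strongest reply is that nothing here breaks a stated rule. Zeros are what proportional allocation yields with few clusters, and without urban shares no misallocation can be shown. That stands: the fault is in the rule, which has no floor, not in how the table applies it. The table is also provisional, which makes a change cheap. The missing minimum, however, is in the protocol text itself.

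A reader might infer four stronger things that the protocol does not support.

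- *That the urban and provincial estimates fail.* The aim names the country, urban and rural areas separately, and the major administrative regions. It does not promise urban estimates within each province. Eighteen urban clusters still support a national urban estimate, with incomplete coverage.
- *That half of the urban clusters being in Colombo is a distortion.* On the table's own figures Colombo's urban population is 9/12 x 2,324 = 1,743 thousand, and 18% of 20,360 is 3,665. Colombo holds 1,743/3,665 = 48% of it, so 9 of 18 is roughly proportional.
- *That the provincial bias exceeds the stated precision of 0.5%.* That figure is for a country sample of 30,000. A province of 6 or 12 clusters has a much wider interval.
- *That urban shares of 10-20% can be assumed in all four provinces.* If rounding produced the zeros, North-western cannot exceed about 8%, nor North-central or Uva about 17%.

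The Bangladesh floor is a rule for that country only, and its Chittagong Hill Tracts sites are all rural. It is a precedent inside the protocol, not an obligation for Sri Lanka.

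**Conclusion.** The point holds as a coverage gap. Under the draft, any urban residents of 16 of 25 districts, including all 11 in four provinces, cannot be selected, and weighting cannot repair that. This conflicts with the aim of representing urban areas and each major administrative region. The counts are certain because they come straight from Table 2.5.

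The size is uncertain. It rests on nearest-integer rounding and an assumed 5-10 point urban-rural gap. On that basis the provincial bias is up to about 2 points, with only Northern able to go higher, and it may lie within a province's own sampling error. Nationally it is below 1 point. The direction depends on the condition. The gap is worth correcting before sites are drawn, but it does not invalidate the Sri Lankan results.

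**What to change.** Set the number of urban clusters at province level and draw them from the urban GN divisions of all districts in the province, with a minimum of one per province. On the present table this turns one rural cluster into an urban one in each of Northern, North-western, North-central and Uva: four of 100 clusters re-labelled, no extra participants. Drawing across the whole province also gives urban GNs in the five other uncovered districts a chance of selection. The weights should reflect the over-allocation wherever one cluster exceeds the province's proportional urban share.

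The costs are slightly more unequal weights and urban strata with a single cluster, which must be collapsed with others for variance estimation. The floor also presumes that each province has at least one urban GN with a qualifying health facility, since the selection list is restricted to those. A fully proportional reallocation would need urban shares that the protocol does not give.

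If the table is kept, the protocol should state that urban estimates cover only nine districts in five provinces, and that the estimates for the four provinces exclude urban residents.

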2. STUDY OBJECTIVES

This project represents a collaboration between academic and clinical experts in NCD prevention and control from leading institutions in Bangladesh, India, Pakistan, Sri Lanka and the UK. With initial 4-year funding from the UK National Institutes for Health Research, we will pursue a program of translational research in South Asian that aims to:

- Strengthen NCD surveillance systems in Bangladesh, India, Pakistan and Sri Lanka, by establishing a network of >200 surveillance sites across these South Asian countries.
- Using standardised approaches, complete structured assessments on a representative sample of ~160,000 South Asian men and women aged 18+ years, living at the >200 surveillance sites. Collect and store biological samples for epidemiological purposes.
- In the longer-term, continue longitudinal follow-up of the 160,000 people screened, to ascertain fatal and non-fatal NCD outcomes. Thereby enable quantification of NCD risk relationships, including identification and evaluation of disease biomarkers.
- In addition, use a subset of the surveillance sites as Health observatories for evaluation of healthcare interventions targeted at improving prevention and control of T2D and CVD in South Asia.
- Thereby provide the first robust, nationally representative data on the burden of T2D, CVD and their risk factors, and on the quality of care for these major NCDs to quantify needs, in South Asian populations.
- Disseminate the data to relevant stakeholders, include health service providers and policy makers to inform resource allocation and health system priorities. In addition, use the clinical data and biological samples collected, to pursue epidemiological research into aetiological mechanisms underlying the increased risk of T2D and CVD in South Asians.

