For the selection of rural and urban sites within a district, we will make a list of rural and urban Grama Niladhari (GN) divisions having a Primary Medical Care Units (PMCU) or a Divisional Hospital with a healthy lifestyle center. From the list of these GNs we will randomly select the number of surveillance sites needed for the district. If any GN is too large and has more than 1000 population, we will divide the GN into segments based on already existing demarcations in the electoral lists. The segment that has the PMCU/Divisional Hospitals will be our surveillance site. Everyone who meets the inclusion criteria within the selected site will be invited to be a participant of the surveillance.

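### Sri Lanka and Bangladesh can select only areas that hold a health facility, yet the protocol claims national and regional representativeness

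*Protocol*

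**What the plan says.** **Sri Lanka** (section 3, Selection of Surveillance sites). Within each district, "we will make a list of rural and urban Grama Niladhari (GN) divisions having a Primary Medical Care Units (PMCU". A second facility type also admits a division to the list: "or a Divisional Hospital with a healthy lifestyle center". Then: "From the list of these GNs we will randomly select the number of surveillance sites needed for the district". Where a division has more than 1000 people it is segmented, and "The segment that has the PMCU/Divisional Hospitals will be our surveillance site". The 100 sites are allocated to provinces and districts by population size (section 3; Appendix 2, Table 2.5).

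**Bangladesh** (same section). Community clinics are selected within a sub-district, and "The ward in which the CC is located will be our rural surveillance site". Urban sites are the mahallas in which a selected urban dispensary or clinic stands. Above 2000 people, only the segment with the clinic or dispensary is used.

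**The claims.** Section 2: "Thereby provide the first robust, nationally representative data on the burden of T2D, CVD and their risk factors, and on the quality of care". Section 3 promises estimates "from a sample that are representative of the country, rural and urban areas separately and for each of the major administrative regions".

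**The analysis.** Section 7 plans sample weights for the descriptive analysis. Appendix 1 includes, among the indicators to be captured directly, the proportions of people with hypertension, with diabetes and at high cardiovascular risk who receive drug therapy and counselling.

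**The concern.** The number of sites per district is set by the whole population, but the people who can be sampled are only those living where a facility stands. Two layers of exclusion are built in: divisions or wards with no facility, and, inside a large division or ward, every segment except the one with the facility. A design weight is the inverse of a selection probability, so none exists for a unit whose probability is zero. Allocation by province, district and urban or rural stratum balances geography but not access to care.

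The stake is greatest for treatment coverage and quality of care, because a unit enters the frame by having local care. If people living beside a facility are more often diagnosed and treated, figures given to policy makers as national would understate unmet need.

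**Working it through.** **1. Does the frame exclude anyone?** In Sri Lanka a list of divisions that have a facility implies that some do not. For Pakistan, section 3 states that every union council has a basic health unit, so a facility condition there would exclude no council. No such statement is made for Sri Lankan divisions or Bangladeshi wards. In Bangladesh, Table 2.1 shows one eligible dispensary or clinic in each of the Khulna and Sylhet city corporations, and in each that one was taken as the division's only urban site. Any other mahalla in those cities could not have been drawn. Whether every rural Bangladeshi ward has a clinic is not stated; if each did, only the segment rule would exclude people there.

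**2. The protocol's own precision.** Table 4 gives 0.5% at country level (N = 30,000) for hypertension (30%) and diabetes (20%). With half-width = 1.96 x sqrt(p(1 - p)/N):
- hypertension: 1.96 x sqrt(0.3 x 0.7 / 30,000) = 0.52 points
- diabetes: 1.96 x sqrt(0.2 x 0.8 / 30,000) = 0.45 points

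Both reproduce. They measure sampling error in prevalence only.

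**3. The right yardstick for treatment coverage.** Coverage is estimated among cases. With the recruitment target of 30,000 for each country (Table 1) and Table 4 prevalences:
- hypertension: 0.30 x 30,000 = 9,000 cases; at 50% coverage (assumed), 1.96 x 0.5 / sqrt(9,000) = 1.03 points
- diabetes: 0.20 x 30,000 = 6,000 cases; 1.96 x 0.5 / sqrt(6,000) = 1.27 points

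These assume simple random sampling. For Sri Lanka's 100 sites (90 and 60 cases per site) and an assumed intraclass correlation of 0.05, the design effects are 1 + 89 x 0.05 = 5.45 and 1 + 59 x 0.05 = 3.95, giving about 2.4 and 2.5 points.

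**4. Bias from the incomplete frame.** Bias = (1 - f) x d, where f is the share of the population inside the frame and d is coverage inside minus coverage outside. Neither is in the protocol; both are assumed here.

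| f | bias, d = 2 points | bias, d = 10 points | d at which bias = 1.03 (hypertension) | d at which bias = 1.27 (diabetes) |
|---|---|---|---|---|
| 10% | 1.8 | 9.0 | 1.1 | 1.4 |
| 30% | 1.4 | 7.0 | 1.5 | 1.8 |
| 50% | 1.0 | 5.0 | 2.1 | 2.5 |
| 75% | 0.5 | 2.5 | 4.1 | 5.1 |

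The range is 0.5 to 9 points. If the frame holds half the population or less, a difference of about 2 to 2.5 points already matches the simple-random-sampling half-width. If it holds three quarters, a difference of 4 to 5 points is needed.

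**The case against.** The protocol is open about this design. Section 3 says that sites are centred on primary care units, and section 4 has participants attend a nearby facility. That is a sound practical reason for the frame, but it does not make the sample representative of people outside it. The objection makes the defect one of stated scope rather than concealment; it does not remove it.

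The case against any firm statement of size is stronger, and it stands. The protocol bounds neither f nor d. Section 3 describes the Sri Lankan division as the smallest administrative unit and treats more than 1000 people as too large, so residents of an adjoining division may be nearly as close to the same facility, and d could be small. At f = 75% and d = 2 points the bias is 0.5 points, below the sampling half-width.

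Three stronger readings are tempting, and the protocol does not support them:
- A reader might infer that national coverage will certainly be overstated. That is plausible, but no figure compares areas with and without a facility.
- A reader might set the bias against the 0.5% in Table 4. That figure is for prevalence in 30,000 people, not for treatment among 6,000 to 9,000 cases.
- A reader might infer that prevalence is materially biased. The representativeness claim for burden has the same gap in its frame, but if the two kinds of area are alike in disease frequency, prevalence would be little affected.

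**Conclusion.** The point holds as a mismatch between frame and claim. Sri Lanka and Bangladesh sample only facility-hosting areas, and only the facility segment where the area is large, while sections 2 and 3 claim representativeness of the country, of rural and urban areas and of regions. The planned weights cannot close that gap. This follows from the text and needs no assumption.

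The size and direction of any bias cannot be established. The 0.5 to 9 points is an illustration resting on assumed f of 10-75% and d of 2-10 points, to be read against about 1.0 to 1.3 points of sampling error before clustering. It shows that the bias could range from negligible to dominant. Quality-of-care and treatment-coverage indicators carry most of the risk. The rest of the design is not invalidated; the stated inference is wider than the frame.

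**What to change.** In sections 2 and 3, for Sri Lanka and Bangladesh:
1. State the target population as residents of facility-hosting divisions, wards or mahallas, or of their facility segments where the area is segmented. Naming the division or ward alone would still be too broad.
2. Report, from administrative data, the share of each district's population that this frame holds.
3. Remove or qualify the claim of national representativeness, above all for the quality-of-care and treatment indicators in Appendix 1.

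The cost is a narrower claim and a small amount of work linking facility lists to population data. No fieldwork changes.

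If the national claim is to be kept, draw divisions and wards from the full list in each stratum, choose the segment at random with known probability, and assess participants at a nearby facility, as section 4 already allows. This costs more. The facility-segment rule must be replaced, because it has no meaning in an area without a facility, and longer travel may affect the participation of over 70% expected in section 4. Bangladesh would need a new draw, since Table 2.1 already names clinics in its draft list. For Sri Lanka, Table 2.5 shows only cluster counts, so the change may still be possible before any division is drawn.
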